## 15.6. Analysis Populations

## 15.6.1. Safety Analysis Set

The Safety Analysis set will include all subjects who receive any amount of study drug.

## 15.6.2. Intent-to-Treat Analysis Set

The Intent-to-Treat (ITT) Analysis Set for efficacy analyses includes all subjects who received any study drug and have a baseline and at least one post-baseline efficacy assessment.

## 15.6.3. Iron Absorption Analysis Set

The Iron Absorption (IA) Analysis Set will include all ITT subjects who complete Iron Absorption B.

## 15.7. Handling of Missing Data

Missing data will not be imputed for calculation of mean changes and other quantitative analyses since the aim for those analyses is to estimate mean changes and other quantitative outcomes in subjects who remain on treatment. Missing data are assumed missing at random for subjects remaining on treatment at each respective time point.

## 15.8. Analysis of Safety

The safety analysis will include all subjects who receive any amount of study medication. Reported AEs will be coded using the Medical Dictionary for Regulatory Activities (MedDRA). All AEs will be summarized by system organ class and preferred terms within system organ class for overall AEs, for AEs any time during the study. The severity, seriousness, and relationship to study medication will also be summarized in a similar manner. Each AE (based on preferred term) is counted once for a given subject. If the same AE occurred on multiple occasions, the highest severity and least complimentary relationship will be assumed.

The incidence of TEAEs and SAEs will be summarized overall and by the subgroup alone, respectively.

Additionally, laboratory test data, physical examinations, vital signs, and ECGs will be summarized overall and by the subgroup alone, respectively.

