# **7.6.2.** Safety

Safety is assessed using NIH CTCAE v5.0 criteria.

- Tabulate frequency of treatment-emergent adverse events (TEAEs) and SAEs; treatment-related TEAEs and SAEs; TEAEs leading to study discontinuation.
- Summarize vital signs, safety laboratory assessments, ECGs, and physical examination findings.

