#### 14.2. Adverse Events and Serious Adverse Events

In this study, AEs and SAEs will be reported in all subjects from the time the subject signs the ICF until the completion of the safety follow-up/end of study visit. Treatment-emergent AEs and SAEs will be evaluated from study drug dosing until the end of study visit.

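### Section 15.8 bases the severity and seriousness summaries on adverse events from consent onward, so pre-dose events can raise a subject's reported worst grade, although the safety endpoint is defined on treatment-emergent events

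*Combined protocol and SAP*

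**What the plan says.** Section 7.6.2 gives the safety endpoint as: "Tabulate frequency of treatment-emergent adverse events (TEAEs) and SAEs; treatment-related TEAEs and SAEs; TEAEs leading to study discontinuation".

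Section 14.2 separates two windows. For collection, "AEs and SAEs will be reported in all subjects from the time the subject signs the ICF", so recording starts before any study drug. For evaluation, "Treatment-emergent AEs and SAEs will be evaluated from study drug dosing until the end of study visit".

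Section 15.8 analyses all subjects who receive any study medication. It summarises adverse events by system organ class and preferred term "for overall AEs, for AEs any time during the study". It continues: "The severity, seriousness, and relationship to study medication will also be summarized in a similar manner". Each preferred term counts once per subject, and "If the same AE occurred on multiple occasions, the highest severity and least complimentary relationship will be assumed". One later sentence covers TEAEs and SAEs, and it plans their incidence, overall and for the subgroup. Section 15.8 plans no TEAE table by severity and does not mention TEAEs leading to discontinuation.

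**The concern.** Safety and tolerability is the first objective (Section 6), and the study has a single arm, so no control column shows the background rate of events. The severity table is where a reader will look for the tolerability profile of PTG-300. As Section 15.8 is written, the only planned severity table mixes events before the first dose with events on drug.

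The pre-dose period is not quiet. Every subject has a phlebotomy within about 7 days before dosing, and substudy subjects also take oral 57Fe during Screening (Section 7.1.1). Section 5.5 names anemia as the potential risk of the study, and Section 7.2.1 excludes hemoglobin decreases caused by phlebotomy from its dose-reduction criterion. The protocol thus recognises that phlebotomy can look like a drug effect, but Section 15.8 does not set pre-dose events apart.

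**Working it through.** **1. Windows.** Section 7.1 gives Screening up to 3 weeks, treatment up to 24 weeks and follow-up 4 weeks. The sum is 3 + 24 + 4 = 31 weeks, which reproduces the stated total. The treatment-emergent window is 24 + 4 = 28 weeks. The pre-dose share of observation time is at most 3/31 = 9.7%.

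**2. Direction.** Under the worst-grade rule, the reported grade for a subject and preferred term is the maximum over all occurrences counted. Widening the window from treatment-emergent to any time adds occurrences and removes none. The maximum can therefore rise or stay the same, but it cannot fall. A term that occurs only before dosing adds an entry that a TEAE table would not contain. The same holds for having any serious event.

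**3. Relationship.** Section 14.2.1.2 steers events before treatment to the Not related category. The least favourable attribution is kept, so a pre-dose Not related assessment gives way to any on-drug attribution. A correctly assessed pre-dose event cannot worsen this column. If severity and relationship were cross-tabulated, a pre-dose Grade 3 unrelated event and an on-drug Grade 1 possibly related event of the same term would become one entry, Grade 3 and possibly related. Section 15.8 does not say that the two are cross-tabulated.

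**4. Illustrative size.** The documents give no event rates. Assume a constant rate r per subject-week for a table category, full-length Screening, complete follow-up and all 28 planned subjects dosed. The share of subjects counted is 1 − exp(−28r) in the treatment-emergent window and 1 − exp(−31r) at any time.

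| r (assumed) | Treatment-emergent | Any time | Subjects of 28 | Extra subjects |
|---|---|---|---|---|
| 0.002 | 5.4% | 6.0% | 1.52 vs 1.68 | 0.16 |
| 0.005 | 13.1% | 14.4% | 3.66 vs 4.02 | 0.36 |
| 0.01 | 24.4% | 26.7% | 6.84 vs 7.46 | 0.62 |
| 0.03 | 56.8% | 60.5% | 15.91 vs 16.95 | 1.04 |
| 0.05 | 75.3% | 78.8% | 21.10 vs 22.06 | 0.96 |

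The any-time count exceeds the treatment-emergent count by about 0.2 to 1 subject per category, or about 5% to 10% in relative terms. Each affected subject moves a cell by 1/28 = 3.6 percentage points.

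**The case against.** The strongest reply is that the treatment-emergent tables are already promised. Section 7.6.2 commits to tabulating TEAEs, treatment-related TEAEs and TEAEs leading to discontinuation, and Section 15.8 adds TEAE incidence, so the any-time tables may be read as extra. This stands for incidence and relationship. It does not stand for severity, because neither section plans a TEAE table by grade.

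Three stronger readings are tempting, and the documents do not support them:

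- A reader might infer that the relationship summary is distorted as much as severity. It is not, for the reasons in step 3 of the working, and because Section 7.6.2 already tabulates treatment-related TEAEs.
- A reader might infer that entries joining a pre-dose grade to an on-drug attribution will appear. That needs a cross-tabulation that is not stated, and the same term in the same subject, worse at Screening and recurring on drug.
- A reader might take 9.7% as the share of table entries that precede dosing. It is a share of time at maximum Screening length, or of events if the rate is constant. The tables count subjects once per term.

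Other points also limit the effect. Only dosed subjects are analysed, and exclusion criteria 5 and 6 would keep out some subjects with serious Screening events, which weakens the seriousness argument. The error can overstate harm but not hide it, in an exploratory and largely descriptive study. Section 15 also says that a detailed SAP will follow and take precedence. That SAP could settle the matter, but the supplied document contains no separate SAP text on safety, so Section 15.8 is the rule available.

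**Conclusion.** The point holds for severity and seriousness. Followed as written, Section 15.8 lets pre-dose events raise a subject's worst grade and never lower it, and it offers no treatment-emergent severity table beside it. For seriousness the case is somewhat weaker. Section 7.6.2 does not plainly limit SAEs to treatment-emergent ones, and that limit comes from Section 14.2.

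The size is unknown and probably small. The figure of 0.2 to 1 subject of 28 rests on assumed constant rates of 0.002 to 0.05 per subject-week. It measures extra subjects counted in a category, not how often a worst grade would actually change. The documents do not support a claim that the severity profile will be materially inflated, only that it can be raised. The correction is still worth making, because the bias has one direction, bears on the first objective and is cheap to remove.

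**What to change.** Change Section 15.8, or the corresponding SAP text, as follows:

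- Base the severity, seriousness and relationship summaries on TEAEs as defined in Section 14.2.
- Apply the once-per-subject, worst-case rule to occurrences within the treatment-emergent window only.
- Where severity and relationship are shown together, take both from the same occurrence.
- List adverse events from consent to first dose separately.

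The cost is analysis-plan and table-shell wording plus one extra listing. No new data are needed, because Section 14.3 already requires the time of onset to be recorded. The change removes only pre-dose events. Events from on-study phlebotomy (Section 7.1.2) and from Iron Absorption B (Section 7.1.3) fall after dosing and remain in the treatment-emergent tables.

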## 15.9. Analyses of Pharmacokinetics and Pharmacodynamics

PK: Concentrations of PTG-300 by dose regimen will be estimated. In addition, concentrations will be reported by time point.

PD: Fe absorption will be estimated using the AUC in the subgroup of subjects who complete both iron absorption treatments. Change from baseline in serum iron parameters (serum iron, transferrin, serum ferritin, TSAT) and sTfR will be estimated.

In general, descriptive statistics, including the numbers subjects [n], means, standard deviations [SD], medians, minimums, maximums will be provided for PK parameters as well as for the PD parameters.

## 15.10. Exploratory Endpoints

- Effects of ADA on safety and efficacy.
- The relationship between PTG-300 pharmacokinetics and pharmacodynamics and efficacy will be explored.

# 16. ADMINISTRATIVE PROCEDURES AND ETHICAL CONSIDERATIONS

## 16.1. Study Monitoring

At intervals during the study, as well as after the completion of subject enrollment, the study center will be monitored by a clinical research associate (CRA) for compliance, which will include ensuring that study procedures are being followed, ensuring that accurate and complete data are recorded on CRFs, and reviewing source documentation and drug accountability records. The study will be conducted according to the principles of GCP.

## 16.2. Audits and Inspections

Authorized representatives of Protagonist, a regulatory authority, an Independent Ethics Committee or an Institutional Review Board may visit the site to perform audits or inspections, including source data verification. The purpose of a Protagonist audit or inspection is to systematically and independently examine all study-related activities and documents to determine whether these activities were conducted, and data were recorded, analyzed, and accurately reported according to the protocol, Good Clinical Practice guidelines of the International Conference on Harmonization (ICH E6 (R2)), and any other applicable regulatory requirements in the country where the trial takes place. The investigator should contact Protagonist immediately if contacted by a regulatory agency about an inspection.

## 16.3. Institutional Review Board (IRB) Approval

Prior to commencement of the study, written approval is required by the relevant IRB responsible for the investigational site.

## 16.4. Guidelines for Good Clinical Practice

This study will be conducted in accordance with principles of Good Clinical Practice (GCP) as promulgated by the ICH, and applicable regulatory requirements in the country where the trial takes place. Good Clinical Practice is an international ethical and scientific quality standard for designing, conducting, recording, and reporting trials that involve the participation of human subjects. Compliance with this standard provides public assurance that the rights, safety, and well-being of human subjects are protected under current ethical principles, and that the clinical trial data are credible. Current GCP standards may be found in ICH Guidance E6 (R2). This guidance describes the principles of GCP and the obligations of the institutional review board (IRB), the Investigator and the Sponsor in conducting this study in accordance with those principles.

#### **16.5.** Ethics

#### 16.5.1. Ethics Review

The final study protocol, including the final version of the Informed Consent Form, must be approved or given a favorable opinion in writing by an IRB or IEC as appropriate. Prior to the

commencement of the study, written approval will be required by the relevant IRB/IEC responsible for the investigational site.

In addition, the IRB or IEC must approve all advertising used to recruit subjects for the study. The investigator must submit written approval to Protagonist before he or she can enroll any patient/subject into the study.

The Principal Investigator is responsible for informing the IRB or IEC of any amendment to the protocol in accordance with local requirements. The protocol must be re-approved by the IRB or IEC upon receipt of amendments and annually, as local regulations require.

The Principal Investigator is also responsible for providing the IRB with reports of any reportable serious adverse drug reactions from any other study conducted with the investigational product. Protagonist will provide this information to the Principal Investigator.

Progress reports and notifications of serious adverse drug reactions will be provided to the IRB or IEC according to local regulations and guidelines.

## 16.5.2. Ethical Conduct of the Study

The study will be performed in accordance with ethical principles that have their origin in the Declaration of Helsinki and are consistent with ICH/Good Clinical Practice and applicable regulatory requirements.

#### 16.5.3. Written Informed Consent

A properly executed, written Informed Consent Form, in compliance with the Declaration of Helsinki, ICH GCP, and United States (US) Code of Federal Regulations for Protection of Human Subjects (21 CFR 50.25[a,b], CFR 50.27, and CFR Part 46, Subpart A), will be explained to and signed by each subject prior to entering the trial. The Investigator will provide a copy of the signed Informed Consent Form to each subject and will maintain a copy in the subject's record file.

## 16.6. Termination of Study

The Sponsor has the right to terminate this study and remove all study material from the site at any time for medical or administrative reasons. In this event, the Sponsor will endeavor to give adequate notice to allow safe withdrawal of subjects from the study.

## **16.7.** Case Report Forms

Site personnel should collect and record data for the study as source documents and transfer the data into the CRF.

The Investigator must ensure that complete data for the clinical study are collected and accurately documented in the appropriate sections of the CRF and adequately supported by the appropriate source documentation. In addition, it is the Investigator's responsibility to provide signatures where requested indicating concurrence with data in the CRF.

## 16.8. Inspection of Records

Protagonist will be allowed to conduct site visits to the investigation facilities for the purpose of monitoring any aspect of the study. The Investigator agrees to allow the monitor to inspect the drug storage area, study drug stocks, drug accountability records, subject charts and study source documents, and other records relative to study conduct.

## 16.9. Retention of Records

International Conference on Harmonization, GCP, and US Food and Drug Administration (FDA) guidelines require that essential documents be retained until at least 2 years after the last approval of a marketing application and until there are no pending or contemplated marketing applications, or at least 2 years have elapsed since the formal discontinuation of clinical development of the investigational product.

However, the essential documents should be retained for a longer period if required by the applicable regulatory requirements or by an agreement with the Sponsor. Records should never be destroyed without written approval from the Sponsor.

If an Investigator leaves the institution, he/she must transfer responsibilities for record retention to another individual willing to accept them. The Investigator must notify the Sponsor in writing of the transfer of study documents before the transfer of the study.

#### 17. PUBLICATION POLICY

The data generated in this clinical study are the exclusive property of Protagonist Therapeutics Inc. and are confidential. Any publication of the results of this study must be authorized by the Protagonist and Protagonist will have the opportunity to review any publications that arise from the investigators before submission for publication.

Publication and reporting of results and outcomes of this trial will be accurate and honest, undertaken with integrity and transparency and in accordance with Protagonist's Publication Policy. Subject confidentiality will be maintained by referring to individual subjects by their identifying code used in the trial. Publication of results will be subjected to fair peer-review.

Authorship on any publication of the results from this study will be based on contributions to study design, enrolment, data analysis, and interpretation of results according to International Committee of Medical Journal Editors guidelines (http://www.icmje.org). All conflicts arising through disputes about authorship will be reviewed by Protagonist.

Acknowledgment will be given to collaborating institutions and hospitals and other individuals and organizations providing finance or facilities.

In the case of no publication, information will only be released to the public and media in accordance with Protagonist's Policy.

## 19. APPENDICES

#### APPENDIX 1. CLINICAL LABORATORY TESTS

#### HEMATOLOGY/CBC

hemoglobin % lymphocytes absolute lymphocytes
hematocrit % monocytes absolute monocytes
red blood cell count % basophils absolute basophils
white blood cell count % eosinophils absolute eosinophils

% neutrophils absolute neutrophils platelet count

#### **CHEMISTRY**

sodium calcium indirect bilirubin

potassium phosphorous alkaline phosphatase

chloride albumin alanine aminotransferase

(ALT, SGPT)

carbon dioxide total protein (AL1, SOF1)

blood urea nitrogen (BUN) uric acid aspartate aminotransferase

creatinine total bilirubin (AST, SGOT)

lactate dehydrogenase

glucose direct bilirubin (LDH)

#### **URINALYSIS**

pH ketones protein

specific gravity microscopic exam (RBC and WBC, only when

indicated)

glucose leukocyte esterase

## PREGNANCY TEST

Serum pregnancy test (to be completed on site) for female subjects of childbearing potential at Screening and at Safety Follow-Up (Week 29)

Urine pregnancy test (to be completed on site) for female subjects of childbearing potential.

## APPENDIX 2. ADDITIONAL LABORATORY TESTS

The following samples to be collected as per Schedule of Assessments (Table 2).

IRON PARAMETERS (PHARMACODYNAMIC PARAMETERS)

serum iron

serum ferritin

transferrin

**TSAT** 

ADDITIONAL ASSESSMENTS

sTfR

hepcidin

**ADA** 

# APPENDIX 3. MEDICAL OUTCOME STUDY QUESTIONNAIRE SHORT FORM HEALTH SURVEY (SF-36)

## Your Health and Well-Being

[figure not shown]
This survey asks for your views about your health. This information will help keep track of how you feel and how well you are able to do your usual activities. Thank you for completing this survey!

For each of the following questions, please mark an  $\boxtimes$  in the one box that best describes your answer.

1. In general, would you say your health is:

2. Compared to one year ago, how would you rate your health in general now?

SF-36v2® Health Survey © 1992, 1996, 2000 Medical Outcomes Trust and QualityMetric Incorporated. All rights reserved. SF-36® is a registered trademark of Medical Outcomes Trust. (SF-36v2® Health Survey Standard, United States (English))

# 3. The following questions are about activities you might do during a typical day. Does your health now limit you in these activities? If so, how much?

		Yes, limited a lot	Yes, limited a little	No, not limited at all
a	Vigorous activities, such as running, lifting heavy objects, participating in strenuous sports	1	2	3
b	Moderate activities, such as moving a table, pushing a vacuum cleaner, bowling, or playing golf	1	2	3
c	Lifting or carrying groceries	1	2	3
d	Climbing several flights of stairs	1	2	3
е	Climbing one flight of stairs	1	2	3
f	Bending, kneeling, or stooping	1	2	3
g	Walking more than a mile	1	2	3
h	Walking several hundred yards	1	2	3
i	Walking one hundred yards	1	2	3
i	Bathing or dressing yourself	1	2	3

SF-36v2® Health Survey © 1992, 1996, 2000 Medical Outcomes Trust and QualityMetric Incorporated. All rights reserved. SF-36® is a registered trademark of Medical Outcomes Trust. (SF-36v2® Health Survey Standard, United States (English))

4. During the past 4 weeks, how much of the time have you had any of the following problems with your work or other regular daily activities as a result of your physical health?

	1/ -					
		All of the time	Most of the time	Some of the time	A little of the time	None of the time
		_			•	
a	Cut down on the amount of time you spent on work or other activities	1	2	3	4	5
b	Accomplished less than you would like	1	2	3	4	5
c	Were limited in the kind of work or other activities	1	2	3	4	5
d	Had difficulty performing the work or other activities (for example, it took extra effort)	1	2	3	4	5

5. During the past 4 weeks, how much of the time have you had any of the following problems with your work or other regular daily activities as a result of any emotional problems (such as feeling depressed or anxious)?

		the time					
a	Cut down on the amount of time you spent on work or other activities	1	2	3	4	5	
Ь	Accomplished less than you would like	1	2	3	4	5	
С	Did work or other activities less carefully than usual	1	2	3	4	5	

SF-36v2\* Health Survey © 1992, 1996, 2000 Medical Outcomes Trust and QualityMetric Incorporated. All rights reserved. SF-36\* is a registered trademark of Medical Outcomes Trust. (SF-36v2\* Health Survey Standard, United States (English))

6. During the past 4 weeks, to what extent has your physical health or emotional problems interfered with your normal social activities with family, friends, neighbors, or groups?

Not at all	Slightly	Moderately	Quite a bit	Extremely
1	2	3	4	5

7. How much bodily pain have you had during the past 4 weeks?

None	Very mild	Mild	Moderate	Severe	Very severe
1	2	3	4	5	6

8. During the past 4 weeks, how much did pain interfere with your normal work (including both work outside the home and housework)?

Not at all	A little bit	Moderately	Quite a bit	Extremely
1	2	3	4	5

 $SF-36v2^{\$}$  Health Survey © 1992, 1996, 2000 Medical Outcomes Trust and QualityMetric Incorporated. All rights reserved.  $SF-36^{\$}$  is a registered trademark of Medical Outcomes Trust. ( $SF-36v2^{\$}$  Health Survey Standard, United States (English))

9. These questions are about how you feel and how things have been with you during the past 4 weeks. For each question, please give the one answer that comes closest to the way you have been feeling. How much of the time during the past 4 weeks...

		All of the time	Most of the time	Some of the time	A little of the time	None of the time
	Did you feel full of life?		2	3		5
ь	Have you been very nervous?		2	3	4	s
e	Have you felt so down in the dumps that nothing could cheer you up?	1	2	3	4	5
d	Have you felt calm and peaceful?	i	2	3	4	5
e	Did you have a lot of energy?	1	2	3	4	5
r	Have you felt downhearted and depressed?		2	3	4	5
	Did you feel wom out?	1	2	3	4	5
h	Have you been happy?		2	3	4	5
i	Did you feel tired?	1	2	3	4	5
10.	During the past 4 weeks , emotional problems interfriends, relatives, etc.)?					
	All of Most of the time the time			A little of the time	None of the time	

3

4

5

SF-36v2® Health Survey © 1992, 1996, 2000 Medical Outcomes Trust and QualityMetric Incorporated. All rights reserved. SF-36® is a registered trademark of Medical Outcomes Trust. (SF-36v2® Health Survey Standard, United States (English))

2

1

